1.2.1. General

Statistical analyses will be performed using two-sided tests.

Data will be summarized by treatment group (and by visit when applicable), with respect to demographic and baseline characteristics, efficacy variables, and safety variables.

Summary statistics will include the mean, N, standard deviation, median, minimum, and maximum values for continuous variables, and frequencies and percentages for categorical variables.

For the analyses of change from baseline, only patients with a baseline and at least one (1) post-baseline measure will be included in the analysis. Unless otherwise specified, baseline is defined as the latest non-missing observation across all the visits in the screening phase before the active study drug begins. Endpoint will be the latest non-missing observation across all the post-baseline visits in the evaluation phase.

Low enrolling sites will be pooled for analysis and the pooling algorithm will be determined prior to breaking the blind. The goal of pooling low enrolling sites is to have a sufficient number of patients per treatment group within a site for the analysis models and for the evaluation of the treatment-by-site interaction for the primary endpoint. Unless otherwise specified, the pooled sites will only be used in the analyses where the site has an effect. The actual sites rather than the pooled sites will be specified in the data listings.

Details of the model and the analyses will be specified in the SAP. All statistical analyses will be performed using SAS®, Version 9.1.3 or higher.

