This is multicenter, randomized, double-blind, placebo-controlled study to be conducted in the United States. Approximately Two Hundred (200) patients diagnosed with mild atopic dermatitis, who satisfy the eligibility criteria for the study, will be randomized to receive either tradipitant 85 mg or matching placebo BID.

The study is divided into two phases: the pre-treatment phase and the evaluation phase. The pre-treatment phase includes a screening and a baseline visit where patients' eligibility for the study will be assessed. Washout of medications will occur during the screening phase.

The evaluation phase includes 8 weeks of randomized, double-blind, placebo-controlled treatment. In-clinic evaluations will occur at Screening, Baseline, and Weeks 2, 4, 6, and 8.

Criteria for Evaluation:

Efficacy:

Efficacy assessments will include:

- Worst Itch Numerical Rating Scale (WI-NRS)
- SCORing Atopic Dermatitis (SCORAD) index
- Validated Investigator Global Assessment scale for Atopic Dermatitis (vIGA-AD)
- Eczema Area and Severity Index (EASI)
- Clinical Global Impression of Change (CGI-C)
- Patient Global Impression of Change (PGI-C)
- Patient Oriented Eczema Measure (POEM)
- Dermatology Life Quality Index (DLQI)
- Patient Benefit Index Pruritus (PBI-P)
- Insomnia Symptom Questionnaire (ISQ)
- Healthy Days Core Module (4 questions) (HRQOL-4)

Safety:

- Safety and tolerability assessments will include the recording of adverse events (AEs), physical examinations, clinical laboratory assessments, vital signs, and electrocardiograms.
- The Columbia-Suicide Severity Scale (C-SSRS) will be used to assess suicidal behavior and ideation.

Table 1: Schedule of Evaluations

Phase	Pre-Tre	Pre-Treatment		Evaluation				
Visit	V1 Screening	V2 Baseline	V3	V4	V5	V6		
Study Day	Up to Day -45	Day 0	Day 14 ¹	Day 28 ¹	Day 42 ¹	Day 56 ¹ or ET		
Informed Consent Form (ICF) ²	X							
Eligibility assessment	X	X						
Patient demography	X							
Medical history	X							
Prior/concomitant medications	X	X	X	X	X	X		
Adverse Event (AE) Assessment ³	X	X	X	X	X	X		
Serum β-HCG (for WOCBP)	X					X		
Urine pregnancy test (for WOCBP)		X	X	X	X			
HbA1c	X							
Hepatitis B/C screen	X							
Drug and alcohol screen	X	X	X	X	X	X		
Hematology, chemistry, and urinalysis ⁴	X	X	X	X		X		
Coagulation ⁴	X							
IgE collection	X	X	X	X	X	X		
Cytokine Panel ⁵	X					X		
Filaggrin Analysis ⁶	X							
Pharmacogenetic (PG) sample ⁶	X							
Pharmacokinetic (PK) sample		X	X	X	X	X		

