Resting 12-lead ECG	X	X	X	X	X	X		
Vital signs and body measurements ⁷	X	X	X	X	X	X		
Physical Examination (PE) ⁸	X	X	X	X	X	X		
Columbia-Suicide Severity Rating Scale (C-SSRS) ⁹	X	X	X	X	X	X		
Medical History of Pruritus Questionnaire		X						
Medical History of Atopy Questionnaire	X							
Pruritus Assessment (incl. NRS, VRS)	X	X	X	X	X	X		
SCORing Atopic Dermatitis (SCORAD) index	X	X	X	X	X	X		
Eczema Area and Severity Index (EASI)	X	X	X	X	X	X		
Validated Investigator Global Assessment scale for Atopic Dermatitis (vIGA-AD)	X	X	X	X	X	X		
Patient Benefit Index – Pruritus (PBI-P) ¹⁰		X	X	X	X	X		

Phase	Pre-Treatment		Evaluation			
Visit	V1 Screening	V2 Baseline	V3	V4	V5	V6
Study Day	Up to Day -45	Day 0	Day 14 ¹	Day 28 ¹	Day 42 ¹	Day 56 ¹ or ET
Patient Global Impression of Change (PGI-C)			X	X	X	X
Clinical Global Impression of Change (CGI-C)			X	X	X	X
Patient Oriented Eczema Measure (POEM)	X	X		X		X
Dermatology Life Quality Index (DLQI)	X	X	X	X	X	X
Insomnia Symptom Questionnaire (ISQ)	X	X		X		X
Healthy Days Core Module (4 questions) (HRQOL-4)	X	X		X		X
Daily Diary	←					*
Photography		X		X		X
Randomization		X				
Study medication dispensation ¹¹		X	X	X	X	
Study medication collection & compliance			X	X	X	X
Daily diary distribution and instruction	X					
Patient daily diary review		X	X	X	X	X

- 1 Within +/- 3 days.
- 2 Informed Consent will be obtained prior to performance of any study procedure(s).
- 3 Adverse Event collection will begin at the time the ICF is signed.
- 4 If elevated liver enzymes are present at any study visit, an unscheduled visit to redraw chemistry and coagulation samples will be completed prior to the next scheduled visit.
- 5 If the V1 cytokine panel sample is missed, the sample should be drawn at the next in-clinic visit (ex. V2).
- 6 If either the V1 Filaggrin or PG sample is missed or unable to be performed for any reason, the samples should be drawn at the next in-clinic visit (ex. V2).
- 7 Body height will only be collected at V1; body weight will be collected at V1, V2, and V6.
- 8 An abbreviated physical examination will be performed at V2-V5 ONLY if clinically indicated.
- 9 The Baseline C-SSRS will occur at V1. The Since Last Visit C-SSRS will occur at all other visits.
- 10 At V2, the Patient Needs Questionnaire (PBI-P(PNQ)) will be administered. The Patient Benefits Questionnaire (PBI-P(PBQ)) will be administered at subsequent visits.

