- 11 Patients will be instructed to take their first dose of study medication on the evening of Day 0 (V2).

ET = Early Termination; WOCBP = Women of Child-bearing Potential; ECG = Electrocardiogram; C-SSRS = Columbia Suicide Severity Rating Scale; NRS = Numeric Rating Scale; VRS = Verbal Response Scale; HbA1c= Haemoglobin A1c or glycated haemoglobin; IgE= Immunoglobulin E

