1.3. Efficacy Data Analysis

1.3.1. Primary Outcome and Methodology

The primary efficacy outcome measure for the double-blind phase will be the WI-NRS responder rate at Week 2. A WI-NRS (worst itch numerical rating scale) responder is defined as a patient achieving at least 4 points reduction from baseline in WI-NRS. The primary statistical method will be the CMH (Cochran–Mantel–Haenszel) test. A detailed description of the primary analysis model and the corresponding sensitivity analysis will be included in the SAP.

As stated previously, any changes in the statistical methods that occur prior to database lock will be documented in the SAP and will not require a protocol amendment.

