1.3.2. Secondary Efficacy Analysis

The secondary efficacy outcomes include:

- WI-NRS;
- DDSS;
- Itch questionnaires including diary WI-NRS and VRS;
- WI-NRS responder at other time points;
- SCORAD;
- EASI;
- Proportion of patients with improvement on SCORAD index of at least 50%, 75% or 90% improvement;
- Proportion of patients with improvement on the EASI of at least 50%, 75% or 90% improvement;
- vIGA-AD;
- PGI-C;
- CGI-C;
- PBI-P;
- HRQOL-4;
- POEM;
- DLQI;
- ISQ;
- Pharmacokinetic-Pharmacodynamic correlation.

Continuous endpoints will be summarized and analyzed using MMRM (mixed effects model repeated measurement). Categorical endpoints will be analyzed by a CMH test. Details of the analysis will be described in the SAP.

Time to event data will be analyzed using the Kaplan-Meier method, and the treatment group differences will be tested by the log-rank test. Details of the analysis will be described in the SAP.

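### Does defining Endpoint as the last available value let early-termination assessments pass as Week 8 results?

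*SAP*

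**What the plan says.** SAP section 1.2.1, in the paragraph on change-from-baseline analyses, states: "Endpoint will be the latest non-missing observation across all the post-baseline visits in the evaluation phase". No later section names an analysis that uses this value, and none excludes it.

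The analyses that are named are these:
- **Primary (SAP 1.3.1):** "The primary efficacy outcome measure for the double-blind phase will be the WI-NRS responder rate at Week 2", tested by CMH.
- **Continuous secondaries (SAP 1.3.2):** "Continuous endpoints will be summarized and analyzed using MMRM".
- **Categorical secondaries (SAP 1.3.2):** "Categorical endpoints will be analyzed by a CMH test". The list includes "WI-NRS responder at other time points" and the 50/75/90% improvement rates on SCORAD and EASI.

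On timing, the Protocol Synopsis (Overall Design) says "In-clinic evaluations will occur at Screening, Baseline, and Weeks 2, 4, 6, and 8". Table 1 heads its last column with Day 56 or ET ("ET = Early Termination"), and its footnote 1 allows 3 days either side of the scheduled day. After baseline, POEM, ISQ and HRQOL-4 are marked only at V4 and V6.

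SAP section 1.2 presents the text as an outline, with the complete methodology to follow in a statistical analysis plan. Sections 1.2.1, 1.3.1 and 1.3.2 repeat that deferral for the models and analyses.

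**The concern.** A last-available-value rule mixes patients seen at Week 8 with patients last seen much earlier. If the mixture is reported as an end-of-treatment result, the bias depends on how many patients leave each arm and how they were doing when they left. It can go either way.

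Two features make this look live here. First, the definition is stated without saying where it applies. Second, early-termination assessments sit in the same column as Day 56, so a program that takes the V6 label at face value would count them as Week 8. The categorical secondaries look most exposed, because no other missing-data rule is given for them. POEM, ISQ and HRQOL-4 look awkward too: a patient who leaves before V4 has at most an early-termination value on those scales, and no V3 slot to hold it.

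At stake would be secondary results that differ according to whether the analyst used Endpoint, the visit label or the actual study day.

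**Working it through.** **1. The plan's own figures.** Inputs from SAP 1.1: 100 per arm; 30% vs 55% response; difference 1.2 with SD 2.6; two-sided 5%.
- Fisher's exact test, by full enumeration: power 93.9%, against a stated approximate 93%.
- t-test: noncentrality 1.2 / (2.6 × √(2/100)) = 3.26 on 198 df, power 90.1%, against a stated 90%.

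Both reproduce, and neither depends on Endpoint.

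**2. Where the text leads if followed as written.** The primary is set at Week 2. An MMRM uses each patient's visit values and needs no carried value. The CMH secondaries are not said to be run at Endpoint. Section 1.2.1 does not equate Endpoint with Week 8. Table 1 is a schedule of procedures: a shared column means that the same assessments are done, not that they are analysed together.

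**3. Timing if the V6 label were taken literally.** The V6 window is 56 - 3 = Day 53 to 56 + 3 = Day 59. A Day 20 early-termination visit is 56 - 20 = 36 days early.

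**4. Size for a responder outcome.** All dropout figures are assumptions. Let dD and dP be dropout on drug and placebo, with 50% and 30% of dropouts responding when last seen. The shift relative to counting dropouts as non-responders is 0.50 × dD - 0.30 × dP.

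| dD / dP | Calculation | Shift (points) |
|---|---|---|
| 10% / 5% | 0.050 - 0.015 | +3.5 |
| 10% / 10% | 0.050 - 0.030 | +2.0 |
| 5% / 10% | 0.025 - 0.030 | -0.5 |
| 10% / 20% | 0.050 - 0.060 | -1.0 |

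The shift is zero at dD/dP = 0.30/0.50 = 0.6. The standard error at 55% vs 30% is √(0.55 × 0.45/100 + 0.30 × 0.70/100) = 0.0676. The range is therefore -0.010/0.0676 = -0.15 to 0.035/0.0676 = +0.52 standard errors. The 55% and 30% are the WI-NRS design rates, borrowed here for scale.

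**5. Size for a continuous outcome.** This applies to a simple V6 comparison, not to the MMRM with values correctly placed. Assume a true difference of 1.2, SD 2.6, and equal early-termination shares in the two arms. If those values carry no treatment effect, a 10% share gives 1.2 × 0.90 = 1.08 (power about 84%) and a 20% share gives 1.2 × 0.80 = 0.96 (about 74%). If they carry half the effect, the figures are 1.14 (about 87%) and 1.08 (about 84%). The comparable starting figure, by the same normal approximation, is 90.4%.

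**6. Whether the obvious replacements do better.**
- *Counting dropouts as non-responders.* Suppose dropouts would have responded at 55% and 30% at Week 8, with 10%/5% dropout. Carrying forward shifts the difference by 0.10 × (0.50 - 0.55) - 0.05 × (0.30 - 0.30) = -0.5 points. Non-response imputation shifts it by -(0.10 × 0.55 - 0.05 × 0.30) = -4.0 points.
- *Moving each early-termination value to the nearest visit at which the scale is scheduled.* A Day 10 POEM value goes to baseline (10 days away, against 18 from V4). A Day 50 value still lands in V6 (6 days, against 8 from V5), as does a Day 43 POEM value (13 days, against 15 from V4). A Day 20 SCORAD value goes to V3 (6 days, against 8 from V4), where it can collide with the value already observed there.

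**The case for a change.** The strongest case for acting is that model details are deferred but the Endpoint definition is not. It is already stated as a rule, without the qualifier attached to the baseline definition beside it. SAP 1.2.2 admits to the Intent-to-Treat set any dosed patient with a single on-treatment efficacy measurement after baseline, so patients with one early value are in the efficacy population. SAP 1.2.3 plans to compare discontinuation for adverse events and for lack of efficacy between arms, so informative dropout is foreseen. SAP 1.2 and 1.3.1 let methods change up to database lock without a protocol amendment. An MMRM is also distorted if a Day 20 value is entered as V6.

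The textual part stands: no use of Endpoint is named, and no analysis windows appear in the supplied documents. It is also true that the documents do not say how someone who leaves before Week 2 enters the primary. None of this shows that the plan produces a wrong Week 8 result. That would take an analyst choosing to run a secondary at Endpoint and call it Week 8, or to ignore visit dates. The freedom to change methods comes with a duty to document changes in the SAP, and SAP 1.7 requires deviations from the statistical plan to be justified in the report.

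**Conclusion.** The concern describes missing detail, not an error. The plan contains an unassigned definition and a shared schedule column, and the supplied text leaves windows and missing-data handling to the full analysis plan. Analysts routinely fill this gap by placing assessments according to actual study day, and the named MMRM needs no carried value. The primary is fixed at Week 2 and the stated power reproduces at 93.9% and 90.1%.

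Any effect is confined to secondary or descriptive end-of-treatment results and is conditional on choices not made in these documents. For responder outcomes the illustration gives -1.0 to +3.5 points, about half a standard error at most. At 10%/5% dropout, the shift goes from +3.5 to -0.5 points when only the benchmark for dropouts changes. In the continuous illustration the power loss is larger (to about 74% at a 20% share with no effect in those values), but it needs early-termination values to be misread as Week 8 outside a properly dated MMRM. Every dropout and last-seen response figure is assumed.

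Nor is there a clear gain from the obvious replacements: non-response imputation is a defensible choice that can shift the difference more than carrying forward does, and nearest-visit mapping misplaces some values. No change to the plan follows.

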1.2.2. Patient Populations for Analysis

The following analysis populations will be defined for this study:

Intent-to-Treat: Any patient randomized into the study that receives a dose of study drug and that has completed at least one post-baseline efficacy measurement while on study medication;

Safety: Any patient randomized into the study that receives a dose of study drug;

Per-Protocol: Any patient who is randomized and receives the protocol required study drug exposure and required protocol processing.

Efficacy analyses will be performed on the Intent-to-Treat population and the Per-Protocol population. Safety summaries will be based on Safety set. Patient characteristics will be presented for all patients randomized.

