1.2. Statistical Methods and Analysis Plan

This section describes the planned statistical analyses in general terms. A complete description of the methodology will be specified in a statistical analysis plan (SAP). Any changes in the statistical methods described in this protocol that occur prior to database lock will be documented in the SAP and will not require a protocol amendment.

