1.2.3. Patient Disposition

Study completion and reasons for discontinuation for all randomized patients in the double-blind phase will be summarized for each treatment group. Discontinuations by reason will be tabulated by visit for each treatment group.

Time to discontinuation due to adverse events, lack of efficacy, and for any reason will be analyzed using Kaplan-Meier survival techniques; the log-rank test will be used for group comparison.

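### The set labelled Intent-to-Treat is a modified ITT, and these documents name no efficacy analysis of all randomised patients

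*SAP*

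**What the plan says.** SAP 1.2.2 puts two conditions on Intent-to-Treat beyond randomisation: at least one dose of study drug, and a patient "that has completed at least one post-baseline efficacy measurement while on study medication". It then assigns the analyses: "Efficacy analyses will be performed on the Intent-to-Treat population and the Per-Protocol population". The full randomised group is used for description only. Section 1.2.2 says "Patient characteristics will be presented for all patients randomized", and section 1.2.3 says "Study completion and reasons for discontinuation for all randomized patients in the double-blind phase will be summarized for each treatment group".

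Section 1.2.1 adds a related rule. For change-from-baseline analyses, "only patients with a baseline and at least one (1) post-baseline measure will be included in the analysis". The primary outcome in 1.3.1 is the Week 2 WI-NRS responder rate, where response is a fall of at least 4 points from baseline, tested by CMH. Neither section says whether the 1.2.1 rule reaches that outcome.

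Section 1.2.2 does not say which measurements qualify. Section 1.3.2 lists diary WI-NRS among the efficacy outcomes. Table 1 of the protocol synopsis schedules a pruritus assessment at every visit. The first post-baseline visit is Day 14 (within 3 days), and the last visit column also serves as early termination.

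The SAP text describes itself as general and leaves the full method to a later SAP: "Any changes in the statistical methods described in this protocol that occur prior to database lock will be documented in the SAP". Section 1.3.1 likewise defers the detailed primary model and its sensitivity analysis.

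**The concern.** Membership of the primary efficacy set depends on what happens after randomisation. Two kinds of randomised patient can fall out of every named efficacy analysis: those never dosed, and those who stop drug before a qualifying measurement. The second kind matters more. Because the measurement must be taken on drug, a patient who stops in the first days and then attends off drug at Week 2 or early termination can be excluded although a score exists.

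Early stopping can depend on the assigned treatment and on how the patient is doing. If it depends on both, the remaining groups are no longer those that randomisation created. The responder rate is then raised more in the arm that loses more poor responders. Section 1.2.3 plans log-rank comparisons of time to discontinuation, which could reveal unequal loss but would not correct the primary test. The label adds to the problem, because a reader would take an Intent-to-Treat result to include everyone randomised.

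**Working it through.** **Inputs.** SAP 1.1: 100 patients per arm, response 30% on placebo and 55% on drug, two-sided 5% level. SAP 1.3.1: CMH test. The documents give no attrition or exclusion rate, so every loss rate below is assumed.

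**The plan's own figure.** Exact enumeration of the two-sided Fisher test with 100 per arm at 55% and 30% gives power of 93.9%, against the stated approximately 93%. It reproduces. The CMH test (single stratum, no continuity correction) has power 95.5% on the same inputs. Both use all 100 per arm, with no allowance for exclusions.

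**Error rate in the set as defined.** Suppose the true response among all randomised patients is 30% in both arms. Let L be the fraction excluded in an arm and q the response rate among excluded patients, taken as the same in both arms. Then in each arm:

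- patients analysed: n = 100 × (1 − L)
- response in those analysed: p = (0.30 − L × q) / (1 − L)

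With x drug responders, m responders in total and N = n1 + n2, the test rejects when (x − n1·m/N)² / V > 3.841, where V = n1·n2·m·(N − m) / [N²(N − 1)]. Rejection probability is summed over all pairs of binomial outcomes.

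Example, 15% loss on drug and 5% on placebo, q = 0: n = 85 and 95; p = 0.30/0.85 = 35.3% and 0.30/0.95 = 31.6%. That is a false difference of 3.7 points in favour of drug.

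| Loss, drug/placebo | q | Two-sided error | Errors favouring drug (nominal 2.5%) |
|---|---|---|---|
| 5%/5% | 0 | 5.0% | 2.5% |
| 2%/0% | 0 | 5.1% | 3.1% |
| 5%/2% | 0 | 5.4% | 3.6% |
| 10%/5% | 0 | 6.0% | 4.7% |
| 15%/5% | 0 | 7.6% | 7.0% |
| 10%/5% | 15% | 5.4% | 3.6% |
| 15%/5% | 15% | 5.4% | 4.1% |
| 10%/5% | 30% (unrelated to outcome) | 5.2% | 2.7% |
| 15%/5% | 30% (unrelated to outcome) | 4.8% | 2.3% |

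**Keeping everyone and counting missing as non-response.** Here n = 100 and p = 0.30 − L × q. With q = 0, error is 4.9% whatever the loss. With q = 15% it is 5.1% at 10%/5% and 5.6% at 15%/5%. With q = 30% it is 5.6% and 7.5%, read as a test of itch response alone. The excess now favours placebo (4.2% and 6.8% in that direction). This rule therefore fails where the present set holds, and the reverse.

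**Power when missing counts as non-response.** At 5% missing per arm, 55% × 0.95 = 52.25% and 30% × 0.95 = 28.5%. CMH power goes from 95.5% to 93.5%, and Fisher power from 93.9% to 91.5%. With unequal loss unrelated to outcome, CMH power is 86.8% at 10%/5% (49.5% against 28.5%) and 76.3% at 15%/5% (46.75% against 28.5%). The present set gives 93.0% (90 and 95 patients) and 93.2% (85 and 95 patients).

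**The case against.** Four points on the other side carry weight.

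- **Exclusions may be few.** Section 1.2.2 asks for an efficacy measurement, not a clinic visit. Diary WI-NRS is a listed efficacy outcome and the first dose is on the evening of Day 0, so an early diary entry on drug might qualify almost every dosed patient. The documents do not settle this. If it is so, mainly never-dosed patients are lost. With matching capsules and an intact blind, not taking a first dose should not depend on arm, so dropping them should add little bias.
- **The larger figures need large assumptions.** An error of 7.6% needs 15% against 5% excluded and no responders among them. At half the response rate the same losses give 5.4%. This stands.
- **A later SAP may deal with it.** The text allows methods to change before database lock and defers the primary model and its sensitivity analysis. That limits the point to what is written here. It does not remove it, because 1.2.2 states the set and its use outright.
- **Missing Week 2 scores are a separate question.** A patient with one on-drug score but no Week 2 score is already inside the present set. That is right, and it is why redefining the set must come with a missing-data rule. A reader might infer that missing must count as non-response in the primary test. The calculations do not support making that compulsory: it costs power and can shift the result against the arm with more loss.

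The rule in 1.2.1 is weaker support. It is written for change-from-baseline analyses, and its reach to a responder rate is uncertain, so a clarifying sentence is enough.

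**Conclusion.** The point holds as a matter of definition. In these documents the Intent-to-Treat set is a modified ITT, and no named efficacy analysis includes all randomised patients. The consequence is conditional. Bias in the Week 2 test needs exclusions that differ by arm and excluded patients who respond less. Under the assumed losses with no responders among the excluded, error rises to between 5.4% (5%/2%) and 7.6% (15%/5%). With small, equal or outcome-unrelated loss it stays near 5%. The calculation assumes a single-stratum CMH test, fixed loss and the same response among excluded patients in both arms.

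A reader might infer that the primary result will be biased, or that the sample size is wrong. Neither follows: no loss rate is given, and the stated power reproduces on its own inputs. Nor do the documents show that the sponsor has ruled out an all-randomised analysis, since the later SAP was not supplied. This is a cheap improvement of minor-to-moderate weight.

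**What to change.** - **SAP 1.2.2:** define Intent-to-Treat as all randomised patients, analysed as randomised. Drop the dose and on-drug measurement conditions, so that a Week 2 score obtained after stopping drug is used. Rename the present set modified ITT, state whether diary or early-termination scores qualify a patient for it, and keep it with Per-Protocol as supportive.
- **SAP 1.2.1:** state that the post-baseline-measure rule does not remove patients from the primary responder test.
- **SAP 1.3.1:** report the all-randomised Week 2 responder analysis with missing scores counted as non-response, together with a multiple-imputation or tipping-point analysis. Which missing-data rule is primary is the sponsor's choice, to be fixed before unblinding.

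The cost is wording and a little more analysis, with no new data collected. If missing counts as non-response, CMH power falls from 95.5% to about 93.5% at an assumed 5% missing per arm, and the result moves against the arm with more loss.
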